9. RESEARCH METHODS

9.1 STUDY DESIGN

This is an observational cohort study based on existing data.

BOEHRINGER INGELHEIM Group of Companies**NIS Protocol Template****Study number: 1484.0014****Page 12 of 30****Document number: <insert>****9.1.1 Study population**

Study inclusion criteria: All patients ≥ 50 years, with a GA diagnosis in at least one eye, including in the [REDACTED] database identified during the study period (January 2015 to April 2023).

Exclusion criteria: Patients without the information of laterality will be excluded.

No other exclusion criteria are applied for the identification of the study population and description of the patients and eye at baseline.

Additional note:

For certain analysis the patient population will be restricted to those with at least 12, 24, 36, 48, or 60 months of history following diagnosis of GA. For the analysis requiring a VA reading, a restriction to those patients with valid VA readings at the index diagnosis and the respective follow-up times will be applied.

For analysis estimating the size of the GA population relative to other retinal diseases, the same timeframe requirements that the study population will be applied. In this population, any patient in the database will be eligible, and the diagnosis of DME, DR or other conditions may be used for subgroup comparisons.

Primary Disease Definitions

In the [REDACTED] Database, retinal and other diseases are identified using the International Classification of Diseases (ICD), Tenth Revision, Clinical Modification. ICD 10 codes were launched in the USA in October 2015, and are the only version of ICD codes with adequate descriptions of GA and dry AMD severity. As such, only ICD 10 codes will be analyzed in this study and the study period defined above is directly related to the launch of ICD 10 plus a small buffer allowing for physician familiarity.

These codes are entered by the physician at patient visit, with an associated laterality. This, along with the ICD 10 laterality is used in combination to confirm in which eye the disease is occurring. For this study, a patient eye will be considered to have the study disease so long as there is an accompanying ICD code. The primary study diseases to be analyzed are dry AMD, GA and wAMD, and will be identified using the ICD codes in Table 1 below.

Table 1. Study disease definitions-codes.

Study Disease Definitions			
	Dry AMD*	Dry AMD with GA*	wAMD*

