9.2 SETTING**9.2.1 Study sites**

All data in this study is de-identified, from existing electronical health records from the retinal specialist practices included in the [REDACTED] Database (US).

The [REDACTED] database consists of data from a geographically diverse panel of United States based private retina specialists (RS). [REDACTED] has physician coverage from 2015 onwards, totaling up to 360+ physicians coming from 70+ practices. These practices span across the USA geographically, with the regional distribution as follows: Midwest (20%), Northeast (17%), Southeast (27%), Southwest (11%), West (26%). This collection of practices has contributed 2+ million patients and 13+ million patient visits over the lifetime of [REDACTED] and is estimated to account for 15-20% of all retina specialists practicing in the USA. This dataset represents a collection of private practicing retina specialists in the USA, no data is collected from hospital or public institutions.

The [REDACTED] Database therefore includes longitudinal measures of physician findings and patient outcomes. This includes health related outcomes such as deterioration of visual acuity, poor adherence, subretinal fluid, intraocular pressure, and geographic atrophy. Patient phenotypes and individual outcomes can be described by individual comorbidities, demographics, visits, prescriptions, and other relevant clinical characteristics gathered from clinical codes, patient provided information and text mining of patient notes.

Study Subgroups

Following analysis on the overall population, subjects will be placed into subgroups for further analysis. Below are the proposed subgroups which may be subject to modification following data readouts. An initial feasibility will be run to assess each threshold for each subgroup, following which a final subgroup will be chosen. Any analysis (i.e. description of patients characteristics and progression) on subgroups will be defined below.

- Duration of follow up: 1+, 2+ 3+, 4+,5+ years of history
- Newly diagnosed patients with GA vs. patients with an existing GA diagnosis
- Conversion rates over time – Stratify the population into those that either progress/don't progress in the 1+, 2+ 3+, 4+,5+ years of follow up;
- [REDACTED] in the 1, 2, 3, 4 and 5 years of follow up period.
- Patients [REDACTED] that do not in the 1, 2, 3, 4 and 5 years of follow up period.

- GA lesion location (sub foveal vs extrafoveal)
- GA lesion size.

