9.4 DATA SOURCES

Founded in 2014, [REDACTED] is the first-to-market EHR data analytics provider in the retina space. [REDACTED] was founded by practicing retina specialists and data-analytics experts with the mission to provide real-world insights from analyzing retina practices' electronic health data. [REDACTED] database consists of de-identified data from EHRs from a geographically diverse panel of United States based private retina specialists. All data comes exclusively from private retina clinics; [REDACTED] not collect data from hospitals or institutions. [REDACTED]

[REDACTED] by an anonymized patient code assigned by the software vendor. Data from multiple sources are organized into the structured database residing in US-based cloud servers. Data is maintained in a secure, password-protected environment using standards associated with personal health information (PHI).

Data Completeness

The Electronic Medical or Health Record represents the entire patient file as maintained by the treating physician and practice with the exception of diagnostic images. Records are continuous regardless of the physician in the practice treating the patient but only to the extent the patient is treated in the same practice. The file is therefore a complete record of the treatments rendered through the practice.

Data completeness within an EHR is entirely dependent on the treating physician recording diagnostic, treatment and other information. Completion rates vary by data element and depend on the treating physician's opinion of the future utility of the information related to that patient's clinical presentation. Crucial visit information such as Procedures, drugs administered, diagnoses, payer, are required at every visit. Outcomes such as IOP and Visual Acuity are entered at 95+% of visits. Foveal thickness is recorded in approximately 30% of encounters where an OCT scan was taken. [REDACTED] neither adds nor removes information received. [REDACTED] receives the key treatment and outcomes information but does not receive every field contained in an EHR. [REDACTED] does extensive work with physicians analyzing their own data through clinical trials or other projects and have not found inconsistencies between the data and the physician's expectation of the data. This iterative process is an integral step in ensuring data accuracy and completeness of our data.

Capture of Concomitant Medications/Exposure

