9.6 DATA MANAGEMENT

[REDACTED] extracts data weekly from various EHR vendors where it is then stored on secure servers accessible only to [REDACTED]. [REDACTED] has multiple data warehouses where an iterative standardization is applied to the data to combine different sources and ensure data accuracy.

Once all data cleansing and standardizing has been performed by [REDACTED], a static dataset is created specifically for the study to ensure there will be no variation in data for its duration. At this point, data accessible for analysis through Microsoft SQL Server Management Studio 18 and the building of the patient population begins. Only after the study population is completed, and all metrics relevant to the analysis have been identified and extracted in aggregated form to excel for further analysis and output generation. The statistical software used for this analysis will be R – version 3.6.3, which will be used for any statistical analysis

BOEHRINGER INGELHEIM Group of Companies**NIS Protocol Template****Study number: 1484.0014****Page 22 of 30****Document number: <insert>**

performed (t-tests, chi-square test or proportion, Confidence intervals etc.). Graphs and tables will be generated using both R and Excel, where applicable.

No personal data will be provided to Boehringer Ingelheim

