Subgroups will be compared against one another to identify any differences in populations leading to progression. The characteristics will be extracted at the time of assignation to the group i.e. patient do not [REDACTED] in year one is contributing with his characteristics extracted at year 1 to the group (no progressors), that patient [REDACTED] at year 5 is contributing with his characteristics extracted at year 5 to the progressor group.

Summary will include descriptive statistics; continuous variables will be described by absolute numbers, the mean (SD), median and range, while categorical variables will be described using frequency and proportion. For discrete demographics or clinical characteristics, chi-squared test of proportion will be done to assess meaningful difference (standardized mean difference SMD may be used as an alternative), while continuous variables will be analyzed using SMD. Following univariate analysis on each metric, a multivariate logistic regression model will be run including relevant metrics identified in the univariate analysis.

Additional information on the analysis is described below:**Patient Demographics (at index and follow up):**

BOEHRINGER INGELHEIM Group of Companies**NIS Protocol Template****Page 25 of 30****Study number: 1484.0014****Document number: <insert>**

N (%); Age, gender, region; Bilateral status, other eye related diagnosis in study and fellow eye; Distribution by months of follow up; Concomitant illnesses (diabetes, cataract, etc.); Lesion location and size (along with % capture rate)

Progression : Progression of GA over time; Fellow eye AMD status; [REDACTED] (study and fellow eye) Mean (median/IQR) time to conversion; Conversion to GA (fellow eye) Mean (median/IQR) time to conversion; Proportion of patients with wAMD and GA (N, %)

[figure not shown]
Treatment Characteristics (follow up): Number of visits over time; Number of treatments over time, Mean (median) time to study treatment; Type of treatment – Anti-VEGF, Laser, Combination, Mean (median) time on therapy

New cases occurrence and prevalent cases of GA (stratified by index year): N (%)

- Age, gender
- Distribution by months of follow up
- Calculation to the % of patients attending the retinal specialist over the same time period for other retinal conditions i.e. wAMD, DR, dry AMD or DME.

Visual Acuity Outcomes

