As an overall limitation of the dataset, Data in the EHR is recorded by the physician or scribe under the direction of the physician. Physicians do not tend to enter data that is not directly relevant to the patient's current condition and tend not to enter null information. There is no real time validation of the information entered during the encounter either in terms of completeness or accuracy. However, ██████████ works extensively with the physicians providing analysis of their own data. As such, this is a crucial step in the data validation process, as physicians analyzing their own data over the years has provided insights on better coding, data entry and completeness. This limitation will affect the covariates related to comorbidities outside of retina. The current workaround is to use the systemic medications list provided to identify the treatment of these comorbidities (diabetes, hypertension etc.). However, this field also comes with its own limitation of relying on the physician/patient to provide an accurate summary of each patient's medication list.

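### The progressor comparison has no practice term, so practice-level recording and coding habits can appear as patient-level predictors of progression

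*Combined protocol and SAP*

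**What the plan says.** Section 9.7.1 (comparison of progression subgroups) sets out two steps. For discrete variables, "For discrete demographics or clinical characteristics, chi-squared test of proportion will be done to assess meaningful difference"; the same sentence allows standardized mean differences (SMD) instead and assigns SMD alone to continuous variables. Then "a multivariate logistic regression model will be run including relevant metrics identified in the univariate analysis". The stated purpose is to find differences between populations that lead to progression. Section 9.6 adds a general software list: "t-tests, chi-square test or proportion, Confidence intervals etc".

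Section 9.2.1 describes the source as "totaling up to 360+ physicians coming from 70+ practices". Section 9.4 states: "Data completeness within an EHR is entirely dependent on the treating physician recording diagnostic, treatment and other information". Section 9.9 adds that physicians "tend not to enter null information" and says that this affects covariates for comorbidities outside the retina. Disease status is also physician-entered. Under Section 9.1.1, "a patient eye will be considered to have the study disease so long as there is an accompanying ICD code". Section 9.3.2.1 takes lesion location from ICD codes and lesion size from text.

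Region is listed as a descriptive variable. No readable text makes practice or physician a stratum, covariate, random effect or cluster, or names a clustered variance. The definitions of two of the three subgroups are partly blacked out, but the tests for them are legible.

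**The concern.** Both sides of the comparison pass through the same physician's record. Smoking, alcohol use, lens status and systemic comorbidities come from codes, medication lists and free text, and progression comes from codes and text. If practices differ in how fully they record covariates and in how they code disease stage, a pooled test mixes those differences with true patient-level differences.

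Two distinct problems follow:

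- **False precision.** Correlation within practices makes a pooled p-value too small, even when the practice effects on the covariate and on progression are unrelated.
- **Confounding by practice.** If the same habit raises both the recorded covariate and recorded progression, the odds ratio itself is biased.

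Both carry forward, because the univariate step chooses what enters the logistic model. Analysing one study eye per patient does not help, since practice is a level above the patient. At stake is the list of apparent predictors of progression. The descriptive counts are not affected.

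**Working it through.** The plan states no power, alpha, design effect or ICC, so there is no figure of its own to reproduce.

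**Inputs from the documents.** 70+ practices (Section 9.2.1); 72,718 GA patients, of whom 20,503 have visits after 3 years (Section 9.5). With 70 equal practices, m = 72,718/70 = 1,038.8 and 20,503/70 = 292.9 patients per practice.

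**Assumptions.** Two-sided 5% level; ICCs from 0.01 to 0.10; covariate and progression frequencies of 30% each; no true association within any practice.

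**1. Unrelated practice effects.** The design effect for the association is DE = 1 + (m − 1) × ICCx × ICCy, and the actual error rate is 2 × (1 − Φ(1.96/√DE)). For all patients with both ICCs at 0.05, DE = 1 + 1,037.8 × 0.0025 = 3.59 and the error rate is 2 × (1 − Φ(1.034)) = 30%. The simulated ranges run from equal practice sizes to sizes with a coefficient of variation of 0.6.

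| ICC covariate / progression | All 72,718: DE, formula | Simulated | 20,503 after 3 years: DE, formula | Simulated |
|---|---|---|---|---|
| 0.01 / 0.01 | 1.10, 6.2% | 5–8% | 1.03, 5.3% | 5–6% |
| 0.02 / 0.02 | 1.42, 9.9% | 10–12% | 1.12, 6.4% | 6–7% |
| 0.05 / 0.05 | 3.59, 30% | 29–35% | 1.73, 13.6% | 13–16% |
| 0.10 / 0.10 | 11.4, 56% | 55–60% | 3.92, 32% | 31–38% |
| 0.05 / 0.01 | 1.52, 11.2% | 10–14% | 1.15, 6.7% | about 7% |

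A Cochran-Mantel-Haenszel test stratified by practice stayed at about 4–6% in every scenario.

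**2. One habit driving both sides.** If the practice-specific probabilities of covariate and progression move together, the pooled proportion with both is 0.3 × 0.3 + ICC × 0.3 × 0.7.

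- ICC 0.01: cells 0.0921, 0.2079, 0.2079, 0.4921; OR = 0.0921 × 0.4921/0.2079² = 1.05.
- ICC 0.02: cells 0.0942, 0.2058, 0.2058, 0.4942; OR = 1.10.
- ICC 0.05: cells 0.1005, 0.1995, 0.1995, 0.5005; OR = 1.26.

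No sample size enters these odds ratios. Simulation with a progression frequency of 20% gave medians of 1.05, 1.11 and 1.30. These were significant in 72%, 100% and 100% of full-cohort runs, and in 31%, 78% and 100% of 3-year runs. The stratified test again stayed near 5%.

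**3. Intervals, if any are reported.** For one proportion, DE = 1 + (m − 1) × ICC. In the full cohort this is 11.4 at ICC 0.01, so an ordinary interval is √11.4 = 3.4 times too narrow as a statement beyond these practices. At ICC 0.05 it is 52.9, or 7.3 times.

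**The case against.** - **Diagnoses are not discretionary.** Section 9.4 lists them among the items required at every visit, so it does not follow that a thorough practice must record more conversions. This stands in part. It makes equal ICCs on both sides an unfavourable assumption, and the 0.05 / 0.01 row is the better guide where only the covariate is selectively recorded. It does not remove the problem: a required field can still be coded differently between practices, and lesion size comes from text.
- **The full cohort is not the progressor denominator.** Follow-up analyses require at least 12 to 60 months, mean follow-up is 22 months, and the count of 72,718 also used exam notes. This stands. In the 3-year subset at ICC 0.01–0.02, the inflation from unrelated practice effects is negligible.
- **P-values are not the only criterion.** SMD is optional for discrete variables and is the sole measure for continuous ones. With unrelated effects at ICC 0.05, 95% of spurious odds ratios in the full cohort lie within about 0.93–1.08, which an SMD would show as trivial. With a shared habit this protection weakens: at ICC 0.05, covariate frequencies of 0.1005/0.3 = 33.5% and 0.1995/0.7 = 28.5% give an SMD of about 0.05/0.46 = 0.11. The plan sets no SMD threshold.
- **The study is descriptive and declares the limitation.** It does, but this objective still specifies tests, variable selection and a multivariable model, and the declared limitation is not carried into them.

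A reader might also infer that this is a cluster sample whose conversion rates, GA proportions and US extrapolation carry intervals that are too narrow. The documents do not support that. All eligible patients in all contributing practices are included, those results are planned as N (%), no interval is specified for the extrapolation, and confidence intervals appear only in the general software list.

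**Conclusion.** The point holds for the progressor comparison. The clustering, the physician-dependent recording and the absence of a practice term are all in the text. That patients are treated as independent is inferred from standard tests named without any clustering provision; the plan does not say so outright.

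The size is conditional on assumed ICCs. It ranges from negligible (both ICCs near 0.01 and unrelated, 3-year subset) to serious (ICCs of 0.05 or more, or a shared recording habit). A reader might take the rates of 30% and above as the expected outcome, but the documents do not show which ICCs apply. The confounding problem matters more than the false precision, because it biases the estimate and a larger cohort only makes the bias look more certain. The change should be made before any variable is reported as a predictor of progression.

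**What to change.** In Section 9.7.1, compare discrete characteristics with a Cochran-Mantel-Haenszel test stratified by practice. Fit the logistic model with practice as a stratum (conditional logistic regression) or as a fixed effect. Report the pooled result beside each, so that the reader sees how much of an association lies between practices. If Cox models are used for progression, stratify them by practice. Where any confidence interval is reported, use a variance clustered on practice or a practice-level bootstrap. This corrects precision only and does not replace stratification.

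The cost is protocol wording and a few lines of R. The analysis file must carry a de-identified practice code. Its availability is inferred from Sections 9.2.1 and 9.4, which count practices, give their regional distribution and describe records as continuous only within a practice; it should be confirmed with the data vendor. Intervals will be wider, between-practice differences in case mix are set aside, and practices with no variation in the outcome or the characteristic contribute nothing. Differences between physicians within a practice remain.

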7. RATIONALE AND BACKGROUND

GA is the late-stage form of dry age-related macular degeneration (AMD) and responsible for 10-20% of the legally blind cases. Currently, there is only one treatment for GA available for patients, [REDACTED] is not approved by EMA yet and therefore not available for patients in Europe. Patients with wet AMD (wAMD), another advanced form of AMD, can be treated with Anti-VEGF treatment.

Presently, Boehringer Ingelheim (BI) is developing potential treatments for the target population of patients with GA secondary to AMD [REDACTED]

There are many unknowns regarding the natural history of patients with GA, and limited data on the prevalence, incidence, and progression of the disease. Recent results from clinical trials developing treatments for GA [REDACTED] found a substantial number of patients with wAMD in the fellow eye or converting to wAMD (20 to 40%) [REDACTED]

[REDACTED] the [REDACTED] a high rate of conversion to wAMD in the study eye occurred. This high rate of conversion may be influenced by the proportion of patients with wAMD present in the fellow eye. This project aims to provide clarity on the proportion of patients in the real world, with GA, wAMD in both study and fellow eyes, and the conversion rates, describing also functional and imaging results and treatment patterns.

BOEHRINGER INGELHEIM Group of Companies

NIS Protocol Template

Page 11 of 30

Study number: 1484.0014

Document number: <insert>

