9.5 STUDY SIZE

During the development of the protocol and while running the projects viability, a feasibility was run on the database identifying both patients and eyes with Dry AMD, and specifically with GA. This analysis was run using only ICD 10 codes and with the use of exam notes. Actual population counts are subject to change based on the dataset available at first data run, but all analysis will be based on the assumption that population sizes are relative to these numbers.

GEOGRAPHIC ATROPHY (PERIOD >=2016) (ICD 10 + Exam Notes)

# of Patients	72,718
# of Eyes	113,408
Avg months of follow-up	22
# of Patients with visits after 3 years	20,503
# of Eyes with visits after 3 years	31,647

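### Chi-square is the default criterion for a meaningful categorical difference, SMD is optional with no threshold, and model entry is undefined, so at these cohort sizes trivial differences would be called meaningful

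*Combined protocol and SAP*

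**What the plan says.** The text is in section 9.7.1, under the objective of describing and comparing characteristics across progression subgroups.

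- Discrete characteristics: a "chi-squared test of proportion will be done to assess meaningful difference". A parenthesis adds that "standardized mean difference SMD may be used as an alternative".
- Continuous characteristics: "while continuous variables will be analyzed using SMD".
- Model: "a multivariate logistic regression model will be run including relevant metrics identified in the univariate analysis".

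The section gives no significance level, no SMD threshold, no rule for when SMD replaces the test, and no definition of relevant. Section 9.6 lists t-tests, chi-square tests and confidence intervals as planned in R, also without a significance level.

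On size, section 9.5 reports feasibility counts of 72,718 patients and 20,503 patients with visits after 3 years, and states that "all analysis will be based on the assumption that population sizes are relative to these numbers". Section 9.1.1 adds: "For certain analysis the patient population will be restricted to those with at least 12, 24, 36, 48, or 60 months of history".

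**The concern.** The aim of this analysis is to find what distinguishes patients who progress. A chi-square p-value mixes the size of a difference with the number of patients. With tens of thousands of patients it falls below 0.05 for differences that nobody would act on. One comparison table would also hold two yardsticks, a test for categorical rows and an effect size for continuous rows, neither with a stated cut-off.

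The comparisons are repeated at 1, 2, 3, 4 and 5 years, and the number of patients will differ between them. Under a test criterion, a characteristic can move from meaningful to not meaningful only because fewer patients have long follow-up. A reader could take that for a change in the disease.

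The model step adds a second weakness. Choosing covariates by their univariate results in the same data can leave out a variable that matters only jointly with others, and tends to make the retained estimates look more certain than they are. Because relevant is undefined, the choice can also be made after the results are seen.

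**Working it through.** The plan has no power or sample-size calculation to reproduce. The check asks how small a difference the default criterion would flag.

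**Inputs from the plan.** N = 72,718 and N = 20,503 (section 9.5); 20,503 / 72,718 = 28%.

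**Assumptions not in the plan.** Two-sided alpha 0.05; a characteristic present in p = 50% of patients; 20% or 40% progressors, prompted by the range that section 7 reports from clinical trials; an illustrative SMD threshold of 0.1.

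**Formulas.** With n1 progressors and n0 non-progressors:

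- smallest significant difference d = 1.96 × sqrt[p(1−p)(1/n1 + 1/n0)]
- SMD = d / sqrt[p(1−p)], which is d / 0.5 at p = 50%

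Example, N = 72,718 with 20% progressors: n1 = 14,544 and n0 = 58,174, so d = 1.96 × sqrt[0.25 × (1/14,544 + 1/58,174)] = 0.0091, or 0.91 points, and SMD = 0.0091 / 0.5 = 0.018.

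| N | Progressors | n1 / n0 | Difference reaching p<0.05 | SMD |
|---|---|---|---|---|
| 72,718 | 20% | 14,544 / 58,174 | 0.91 points | 0.018 |
| 72,718 | 40% | 29,087 / 43,631 | 0.74 points | 0.015 |
| 20,503 | 20% | 4,101 / 16,402 | 1.71 points | 0.034 |
| 20,503 | 40% | 8,201 / 12,302 | 1.40 points | 0.028 |

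**Comparison with an effect-size rule.** An SMD of 0.1 at p = 50% needs 0.1 × 0.5 = 0.05, or 5 points, whatever the N. The ratios are 5 / 0.74 = 6.8 and 5 / 0.91 = 5.5 in the full cohort, and 5 / 1.40 = 3.6 and 5 / 1.71 = 2.9 in the 3-year group.

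**Same difference, different N.** Take 50% against 51%, an SMD of 0.02. At N = 72,718, p = 0.031 (20% progressors) or 0.008 (40%). At N = 20,503, p = 0.25 or 0.16. The difference is identical and the verdict reverses.

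**Sensitivity.**

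- Prevalence, at N = 72,718 and 20% to 40% progressors: the flagging point is 0.45 to 0.55 points at 10% prevalence and 0.68 to 0.83 points at 30%. An SMD of 0.1 needs about 3.2 and 4.7 points.
- Split: with only 5% progressors and N = 72,718, p<0.05 is still reached at an SMD of 0.033.
- Size: for hypothetical subsets with 20% progressors and 50% prevalence, p<0.05 is reached at an SMD of about 0.07 for N = 5,000 and 0.11 for N = 2,000. The problem fades only in small subsets.

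**The case against.** The plan already permits SMD for categorical variables, and it reports frequencies and proportions, so readers will see how large each difference is. The objective is secondary and descriptive. This stands in part: the remedy is close to hand. But an option without a trigger or threshold leaves the test as the default, and the text ties that test to what counts as meaningful.

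Several stronger readings are tempting, and the documents do not support them.

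- A reader might infer that chi-square significance decides which variables enter the model. The plan says only "including relevant metrics identified in the univariate analysis". Entry by p-value is a plausible guess for categorical variables, but it is not stated, and the univariate step also includes SMD for continuous variables. What can be said is that the rule is undefined and data-driven.
- A reader might infer that continuous variables face a stricter rule. With no SMD threshold stated, strictness cannot be compared.
- A reader might take 20% to 40% as the plan's progression rate. Section 7 reports it from clinical trials, in a partly redacted sentence that also covers wet AMD in the fellow eye. It is only an assumption here.
- A reader might apply 72,718 to every comparison. It is the whole feasibility cohort, counted with ICD-10 codes plus exam notes, and mean follow-up is 22 months. The yearly comparisons may use fewer patients.

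It is also fair to say that if nearly every categorical variable were kept, there would be little selection among them to cause bias. The size of any selection bias has not been calculated. Nor does the plan name an exposure to be adjusted for, so an argument about lost confounders should not be pressed.

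**Conclusion.** The concern holds in this form: a significance test is the default measure of meaningful categorical difference, the SMD option has no threshold, and covariates are chosen by an undefined univariate screen. Under the stated assumptions the default flags differences roughly 3 to 7 times smaller than an SMD of 0.1 would require. The conclusion does not depend on the full cohort, since it persists at 20,503 patients, and it is not sensitive to the assumed split at the full size. It does rest on alpha 0.05, and the 0.1 benchmark is a choice made for this review. The case against the model step rests on the wording and on general reasoning, not on a calculated bias.

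**What to change.** In the progression-subgroup text of section 9.7.1:

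1. Make SMD with a 95% CI and one prespecified threshold (for example an absolute value of 0.1) the criterion for both categorical and continuous characteristics. Drop chi-square as the criterion.
2. Replace univariate selection with a covariate list fixed in advance for each comparison and kept whatever the univariate result. Candidates are age, sex, smoking, diabetes and the ocular comorbidities from section 9.3.3, plus index VA, index lesion location and index fellow-eye wet AMD and GA status, which are described elsewhere in the plan.
3. Leave out any variable that defines the groups or the progression endpoint. Lesion location, for instance, cannot be a covariate in the subfoveal against extrafoveal comparison.
4. State when each covariate is measured. The section now takes characteristics at assignment to a group, whereas this list uses index values for VA, lesion location and fellow-eye status.

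The cost is wording. SMD is already permitted, and no data beyond the variables already planned are needed. P-values stop being the criterion. Covariates with incomplete capture, such as smoking and VA, will reduce the complete cases or need an unknown category, and the plan should say which. The change should be made before results are seen.
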